2 OBJECTIVES

2.1 Primary Objectives

The primary objectives of the study are:

- Phase 1B: To characterize the incidence of dose-limiting toxicities (DLTs) of tabelecleucel in combination with pembrolizumab in subjects with platinum-pretreated, recurrent/metastatic NPC
- To identify the maximum tolerated dose (MTD), or in the absence of an MTD, the recommended phase 2 dose (RP2D) of tabelecleucel when administered in combination with pembrolizumab
- Phase 2: To evaluate the objective response rate (ORR), defined as a CR or PR confirmed ≥ 28 days from the initial response assessment showing a response obtained following administration of the combination of tabelecleucel and pembrolizumab, where the Response Evaluation Criteria in Solid Tumors (RECIST) 1.1 response is determined using an independent radiographic review (IRR)
- For both phase 1B and phase 2: To characterize the safety profile of tabelecleucel in combination with pembrolizumab in the NPC subject population

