6.3 Treatment/Consolidation Phase (21-day Cycles)

All subjects will receive 2 treatment cycles (21-day), and depending on their response to treatment, subjects may receive additional treatment and/or consolidation cycles (21-day), refer to Section [15.2](#). During treatment and consolidation cycles, subjects will receive tabelecleucel on Day 1, Day 8 (± 2), and Day 15 (± 2) and pembrolizumab on Day 1 and have a response assessment within 7 days after Cycle 2 Day 15 and every treatment/consolidation cycle thereafter.

6.3.1 Treatment/Consolidation: Day 1

- Physical examination including weight
- AEs

- Concomitant medications
- Hematology panel: CBC with platelet count and differential
- Abbreviated chemistry panel: serum creatinine, TBILI, ALT, AST, alkaline phosphatase, glucose (fasting) and tests of thyroid function (TSH, T3, and T4)
- **Cycle 1 and Cycle 2 only:** **CCI**
[REDACTED]
[REDACTED]
[REDACTED]
- **Cycle 2 and subsequent cycles:** **CCI**
[REDACTED]
- Investigational product infusions:
 - Pembrolizumab will be administered prior to tabelecleucel
 - Tabelecleucel will be administered 1 hour (\pm 10 minutes) after completion of the administration of pembrolizumab only if no infusion reactions related to pembrolizumab are observed/reported or in the case of such a reaction, the subject has recovered
- Vital signs (body temperature, BP, HR, and respiratory rates) at the following times:
 - immediately before the pembrolizumab infusion
 - within 10 minutes following the conclusion of the pembrolizumab infusion
 - immediately before the tabelecleucel infusion
 - within 10 minutes following the conclusion of the tabelecleucel infusion
 - 1 hour (\pm 10 minutes) after initiation of the tabelecleucel infusion
 - **Cycle 1 only:** 2 hours (\pm 10 minutes) after initiation of the tabelecleucel infusion
 - If the subject experiences symptoms/signs of an infusion reaction, follow-up may be longer, as clinically indicated.

6.3.2 *Treatment/Consolidation: Day 8 and Day 15*

- Physical examination including weight
- Concomitant medications
- AEs
- **CCI**
[REDACTED]
- **Cohort 1, checkpoint inhibitor (PD-1/PD-L1) failed subjects only, at least 1 day after Cycle 1 Day 8 and prior to Cycle 1 Day 15:** tumor/active site biopsy as described in Section 7.2 (central laboratory); hematology and coagulation panels must be performed prior to biopsy
- **Cohort 1, Day 15 only,** Hematology panel: CBC with platelet count and differential

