6.5 End-of-Treatment Visit

An End-of-Treatment visit will be performed 30 ± 5 days after the last dose of investigational product (tabelecleucel and/or pembrolizumab) for all subjects, including those who discontinue early from treatment, consolidation, and/or maintenance. The following assessments/procedures will be performed:

- Physical examination including weight
- Concomitant medications
- AEs
- Vital signs (body temperature, BP, HR, and respiratory rate)
- Hematology: CBC with platelet count and differential
- Full chemistry panel: sodium, potassium, chloride, total carbon dioxide, BUN, creatinine, glucose (fasting), total calcium, albumin, total protein, serum creatinine, TBIL, ALT, AST, alkaline phosphatase, and tests of thyroid function (TSH, T3, and T4)
- CMV antibody (if negative at baseline)
- Pregnancy test for women of childbearing potential (serum)
- Performance status: ECOG for subjects > 16 years of age or Lansky score for subjects 12 to 16 years of age
- **CCI** [REDACTED]
[REDACTED]
- **CCI** [REDACTED]
- **Only if within 30 days from the last dose of tablecleucel:** **CCI** [REDACTED]
[REDACTED]
[REDACTED]

- Radiographic assessments (including CT with contrast or MRI) as described in Section 7.1

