All scheduled images for all study subjects from the study sites will be submitted to the central imaging vendor for IRR. In addition, images (including via other modalities) that are obtained at an unscheduled time point to determine disease progression, as well as imaging obtained for other reasons, but captures radiologic progression based on investigator assessment, should also be submitted to the central imaging vendor for IRR.

7.1.2.1 *Initial Tumor Imaging*

Initial tumor imaging at screening must be performed prior to the date of the first dose of investigational product. The study site study team must review screening images to confirm the subject has measurable disease per RECIST 1.1. The screening images must be submitted to the IRR vendor for retrospective confirmation of measurable disease per RECIST 1.1 for eligibility prior to the date of the first dose of investigational product. Tumor imaging performed as part of routine clinical management is acceptable for use as screening tumor imaging if it is of diagnostic quality and can be assessed by the central imaging vendor.

If brain imaging is performed to document the stability of existing metastases, MRI should be used if possible. If MRI is medically contraindicated, CT with contrast is an acceptable alternative.

7.1.2.2 *Tumor Imaging During the Study*

The first on study imaging assessment should be performed after Treatment Cycle 2 Day 15 between Days 16 to 21, and thereafter, after each treatment and consolidation cycle Day 15 between Days 16 to 21. Subsequent tumor imaging should be performed during the Maintenance Phase on Day 77 (\pm 2 days) of each cycle, at the end-of-treatment (30 \pm 5 days after the last dose of investigational product), and during the Quarterly follow-up phase (every 90 \pm 14 days), or more frequently if clinically indicated.

Objective response should be confirmed by a repeat imaging assessment. Tumor imaging to confirm an initial treatment response of PR or CR will occur during the subsequent consolidation cycle.

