u) Cohort 1, checkpoint inhibitor (PD-1/PD-L1) failed subjects, and Cohort 2 (optional): at least 1 day after Cycle 1 Day 8 and prior to Cycle 1 Day 15 core needle, incisional or excisional biopsy is required; hematology and coagulation panels must be performed prior to biopsy. NOTE: Fine needle aspirate is not considered adequate for the purposes of this biopsy. v) Radiographic assessments include MRI or CT with contrast. w) Cohort 1, checkpoint inhibitor (PD-1/PD-L1) failed subjects only: initial evidence of progressive disease with confirmation assessment for retrospective analysis at a central vendor. x) Radiographic assessments will be performed at Screening and between Day 16 to Day 21 of Treatment/Consolidation Cycle 2 and beyond. During the Maintenance Phase, radiographic assessments will be performed on Day 77 (\pm 2 days) of each 84-day cycle. Radiographic assessments will also be performed at EOT and during Quarterly Follow-up for subjects who have achieved a CR, PR, or have SD but did not complete maintenance cycles or had disease progression. y) Pembrolizumab will be administered prior to tabelecleucel. During treatment/consolidation cycles, pembrolizumab will be administered on Day 1 (unless the subject has confirmed disease progression) and tabelecleucel on Day 1, Day 8 and Day 15 of each cycle. During the maintenance cycles, pembrolizumab will be administered on Day 1, Day 21, Day 42, and Day 63, and tabelecleucel on Day 1 of each cycle. Tabelecleucel will be administered 1 hour (\pm 10 minutes) after the administration of pembrolizumab only if no infusion reactions related to pembrolizumab are observed/reported or in the case of such a reaction, the subject has recovered.											

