15.2.2 Stable Disease after the Initial Two Treatment Cycles

A subject who has SD after the initial 2 treatment cycles will receive Switch Therapy, ie a treatment cycle with tablecleucel with a different HLA restriction, if an appropriately matched product is available on Days 1, 8, and 15 and pembrolizumab on Day 1 and then a response assessment at the Observation Visit (refer to [Figure 1](#)). Subsequent treatment is dependent on the response as follows:

- CR or PR: The subject will receive a consolidation cycle with tabelecleucel with the same HLA restriction on Days 1, 8, and 15 and pembrolizumab on Day 1 followed by a response assessment at the Observation Visit. The subject will then receive maintenance cycles (84-day) of combination immunotherapy (pembrolizumab on Days 1, 21, 42, and 63 with tabelecleucel with the same HLA restriction on Day 1) and a response assessment at Day 77. Maintenance cycles will continue until disease progression, unacceptable toxicity, or a total of 35 pembrolizumab infusions (including for treatment, consolidation, and maintenance) have been given. The subject will then complete an End-of-Treatment visit with a response assessment at 30 days after the last dose of investigational product, and then enter Quarterly Follow-up for 12 months from last dose of investigational product or until disease progression.
- SD: The subject will receive another treatment cycle with tabelecleucel with the same HLA restriction on Days 1, 8, and 15 and pembrolizumab on Day 1 followed by a response assessment at the Observation Visit. If the response is CR, PR, or SD, the subject will enter receive maintenance cycles. If the response is cPD, the subject will complete an End-of-Treatment visit (30 days after the last investigational product dose) and enter Quarterly Follow-up for 12 months after the last investigational product dose.
- uPD: The subject will receive another treatment cycle with tabelecleucel with the same HLA restriction on Days 1, 8, and 15 and pembrolizumab on Day 1 followed by a response assessment at the Observation Visit. As described above, if the response is CR, PR, or SD, the subject will receive maintenance cycles. If the response is cPD, the subject will complete an End-of-Treatment visit (30 days after the last investigational product dose) and enter Quarterly Follow-up for 12 months after the last investigational product dose.

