15.2.3 Unconfirmed Progressive Disease after the Initial Two Treatment Cycles

A subject who has uPD after the initial 2 treatment cycles will receive another treatment cycle with tabelecleucel with the same HLA restriction on Days 1, 8, and 15 and pembrolizumab on Day 1 and then a response assessment at the Observation Visit (refer to [Figure 1](#)). Subsequent treatment is dependent on the response as follows:

- CR or PR: The subject will then receive maintenance cycles (84-day) of combination immunotherapy (pembrolizumab on Days 1, 21, 42, and 63 with tabelecleucel with the same HLA restriction on Day 1) and a response assessment at Day 77. Maintenance cycles will continue until disease progression, unacceptable toxicity, or a total of 35 pembrolizumab infusions (including for treatment, consolidation, and maintenance) have been given. The subject will then complete an End-of-Treatment visit with a response assessment at 30 days after the last dose of investigational product, and then

enter Quarterly Follow-up for 12 months from last dose of investigational product or until disease progression.

- SD: The subject will receive Switch Therapy, ie a treatment cycle with tabelecleucel with a different HLA restriction, if an appropriately matched product is available on Days 1, 8, and 15 followed by a response assessment at the Observation Visit. If the response is CR, PR, or SD, the subject will receive maintenance cycles. If the response is cPD, the subject will complete an End-of-Treatment visit and enter Quarterly Follow-up for 12 months after the last investigational product dose.
- cPD: The subject will discontinue pembrolizumab and receive Switch Therapy, ie a treatment cycle with tabelecleucel with a different HLA restriction, if an appropriately matched product is available on Days 1, 8, and 15 followed by a response assessment at the Observation Visit. Subsequent treatment is dependent on the response as follows:
 - CR, PR, or SD: The subject will receive a consolidation cycle with tabelecleucel with the same HLA restriction on Days 1, 8, and 15 followed by a response assessment at the Observation Visit. The subject will then complete an End-of-Treatment visit with a response assessment at 30 days after the last dose of investigational product, and then enter Quarterly Follow-up for 12 months from last dose of investigational product or until disease progression.

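### On the nominal schedule the scan named to confirm a response comes 16 to 26 days after first response, short of the 28 days in the ORR definition, and the SAP does not say whether its ORR is confirmed

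*Protocol*

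**What the plan says.** The protocol synopsis and Protocol Section 2.1 define ORR as a CR or PR "confirmed ≥ 28 days from the initial response assessment showing a response". SAP Section 2.1.1 repeats this. In all three places the text is attached to the Phase 2 objective, with response read by independent radiographic review.

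Protocol Section 7.1.2.2 places the first on-study scan in Cycle 2 and later scans "after each treatment and consolidation cycle Day 15 between Days 16 to 21". Note x to the schedule in Section 15.1 agrees: "Radiographic assessments will be performed at Screening and between Day 16 to Day 21 of Treatment/Consolidation Cycle 2 and beyond". Section 6.3 words the window differently; subjects are to "have a response assessment within 7 days after Cycle 2 Day 15 and every treatment/consolidation cycle thereafter". On confirmation, Section 7.1.2.2 says: "Tumor imaging to confirm an initial treatment response of PR or CR will occur during the subsequent consolidation cycle".

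Not every responder has a consolidation cycle. In Section 15.2.3, for a subject with unconfirmed progression after Cycle 2 who then responds, the rule is "CR or PR: The subject will then receive maintenance cycles (84-day) of combination immunotherapy". In the same section, a subject who is then stable, switches product and responds also goes to maintenance. In Section 15.2.2, after stable disease, a switch, and then stable disease or unconfirmed progression, one more treatment cycle follows; the stable-disease branch reads "If the response is CR, PR, or SD, the subject will enter receive maintenance cycles", and the unconfirmed-progression branch has the same rule.

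For subjects who finish or stop treatment, Section 6.5 says "An End-of-Treatment visit will be performed 30 ± 5 days after the last dose of investigational product", with imaging. Section 7.1.2.3 makes that imaging non-mandatory if a scan was done within 4 weeks before discontinuation.

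SAP Section 8.1.1 defines response by best overall response (BOR) of CR or PR. It does not mention confirmation, and it leaves out disease assessments made in the follow-up stage. SAP Section 8 has the investigators make the assessments and analyses the two sub-cohorts separately.

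**The concern.** A stated procedure should deliver the stated endpoint. Here the protocol names one scan as the confirming scan, and on the nominal schedule that scan comes too early to satisfy the interval. A responder who progresses or leaves before a later qualifying scan would not count as confirmed, even though the named confirming scan had been done.

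The SAP does not settle the matter. Two analysts could follow Section 8.1.1 and report different ORRs from the same data, one confirmed and one not, or one counting End-of-Treatment (EOT) scans and one not. SAP Section 3.2 limits the efficacy summary to ORR, so a reader of the study report could not tell what that figure means.

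**Working it through.** The documents give no figure for the interval between the two scans, so there is none to reproduce. The one computed ORR design figure, 90% power in Protocol Section 9.5, does reproduce: with n = 36 and rejection at 13 or more responses, the exact one-sided alpha at 20% is 0.018 and power at 45% is 89.3%. It is not in question here.

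**Inputs.** 21-day cycles (Protocol 5.2). Scans on Days 16–21 from Cycle 2 (7.1.2.2, 15.1). Maintenance starts 21 days after Day 1 of the previous cycle (6.4), with a scan on Day 77 ± 2. EOT is 30 ± 5 days after last dose (6.5). Quarterly Follow-up is every 90 ± 14 days after last dose (6.6). Day 15 dosing has a ± 2 window. The windows are treated as independent.

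**Calendar, with Cycle 1 Day 1 as day 1.** Cycle 2 scan: days 37–42. Cycle 3 scan: days 58–63. Maintenance Day 1 after Cycle 3: day 64, so Day 77 ± 2 is days 138–142.

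**Gap from first response scan to later scan** (shortest = earliest later scan minus latest response scan; longest = the reverse):

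| Later scan | Shortest | Longest | Meets 28 days? |
|---|---|---|---|
| Consolidation, Days 16–21 | 58 − 42 = 16 | 63 − 37 = 26 | No |
| Consolidation, Days 16–22 (Section 6.3 wording, nominal Day 15) | 15 | 27 | No |
| Maintenance Day 77, via consolidation | 138 − 42 = 96 | 142 − 37 = 105 | Yes |
| Maintenance Day 77, no consolidation (Cycle 3 response) | 138 − 63 = 75 | 142 − 58 = 84 | Yes |
| EOT, last dose in consolidation (days 55–59, EOT days 80–94) | 80 − 42 = 38 | 94 − 37 = 57 | Yes |
| EOT, last dose in the responding cycle (days 34–38, EOT days 59–73) | 59 − 42 = 17 | 73 − 37 = 36 | Sometimes |
| Quarterly Follow-up, last dose in consolidation (days 131–163) | 131 − 42 = 89 | 163 − 37 = 126 | Yes, but SAP 8.1.1 leaves out follow-up |
| Quarterly Follow-up, last dose in the responding cycle (days 110–142) | 110 − 42 = 68 | 142 − 37 = 105 | Yes, same exclusion |

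The gaps are the same if the response appears one cycle later and the rest of the path shifts with it. None of the 6 × 6 = 36 day combinations for the consolidation scan reaches 28.

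**What would reach 28.** If the consolidation cycle starts 2 days late, 1 of the 36 combinations reaches 28; a 12-day delay is needed before all do. Stacking the ± 2 dosing window on the 7-day wording puts scans on Days 14–24 and the gap at 11–31 days, which departs from the stated Days 16–21.

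**The EOT waiver.** A consolidation scan on days 58–63 lies within 4 weeks of any discontinuation date up to days 86–91 (58 + 28 to 63 + 28). The scan that is too early to confirm can therefore excuse the one that would.

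**Size.** Assume the requirement of at least 6 refractory subjects was met among the 12. The PD-1/PD-L1 failure group is then 6–12 subjects and the naïve group at most 6. One subject who counts under BOR but not under the 28-day rule moves ORR by 100/12 = 8.3 to 100/6 = 16.7 points in the first group and by at least 16.7 points in the second. As an illustration with n = 6, 2/6 is 33% (exact 95% CI 4–78) and 1/6 is 17% (0.4–64).

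**The case against.** The strongest reply is that the two halves of this point rest on different readings. The 28-day text is labelled Phase 2 in both documents, and SAP Section 1 says the study ended with Phase 1B. If the definition belongs to Phase 2 only, the scan conflict touches no reported result. If it carries over, SAP Section 2.1.1 supplies the interval. This stands in part: on either reading the protocol conflict has limited effect on the study report. But Section 8.1.1 does not say which reading applies, and that is what needs to be stated.

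A reader might infer that the consolidation scan can never confirm a response. The documents do not support that. Section 5.2.1 allows dosing interruptions with return within 3 weeks, Section 7.1.2.2 allows more frequent imaging when clinically indicated, and the looser window wording can stretch the gap. The mismatch is one of the nominal schedule.

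A reader might also infer that every responder after progression lacks a consolidation scan. That is not so. After confirmed progression and a switch (the last branch of Section 15.2.3, and Section 15.2.4), a responder has a consolidation cycle and then EOT with a response assessment. These subjects never enter maintenance, and EOT at 38–57 days is their next scheduled qualifying scan.

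Finally, Section 7.1.2.3 asks for every effort to keep the on-treatment scan schedule in subjects who stop without progression. That eases the problem but guarantees no scan at a qualifying time.

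**Conclusion.** Wrong as written, minor. On the nominal schedule the scan that Section 7.1.2.2 names comes 16–26 days after first response (15–27 under Section 6.3 with a nominal Day 15), against a definition of at least 28. Three kinds of responder have no consolidation scan at all: unconfirmed progression then response; unconfirmed progression, stable disease, switch, then response; and stable disease, switch, stable disease or unconfirmed progression, then response.

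It would go too far to say that the ORR cannot be confirmed, or that the reported ORR is known to be inflated. Sustained responses can be confirmed at Maintenance Day 77, or at EOT where that scan is late enough and not waived. The documents do not give the number of responders who would be lost. SAP Section 8.1.1 is silent on confirmation; it does not declare the ORR unconfirmed. The exclusion of follow-up assessments is also unclear, because the SAP does not say whether EOT belongs to that stage. If ORR is to be confirmed and EOT is left out, responders on the confirmed-progression and switch branches have no scheduled scan that counts.

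The practical effect is small: 12 subjects, investigator assessment, and no efficacy hypothesis (SAP 6.2). The point shifts under working depend on the assumed sub-cohort sizes and are illustrations, not estimates.

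**What to change.** No scan and no treatment path needs to change.

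- **Protocol Section 7.1.2.2**, to reconcile it with the synopsis and Section 2.1: state that a response is confirmed by the first scan (scheduled, unscheduled or EOT) showing CR or PR at least 28 days after the first response scan, with no intervening progressive disease and no new anti-NPC therapy, and that this scan is submitted for independent review. Without the progression condition, a PR followed by progression and a later PR would count as confirmed. The submission clause is needed because Section 7.1.2 covers scheduled images and unscheduled images bearing on progression, but does not mention an unscheduled scan done to confirm a response.
- **SAP Section 8.1.1**, the change that affects the study report: report by sub-cohort the ORR confirmed at 28 days or more on that rule, counting EOT scans and excluding only Quarterly Follow-up. Put it beside the unconfirmed BOR-based ORR, with each labelled. List for each responder the days from first response to confirming scan.

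The cost is one replaced protocol sentence, one clarified SAP paragraph, one table row and one listing column. With the study terminated, the protocol edit is a consistency correction. The downside is that the confirmed ORR may be lower than the BOR-based one. The change does not shorten the wait for the Day 77 scan, so a response lost before then stays unconfirmed, but the report will show it.
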